5.2. Exclusion Criteria

Participants are excluded from the study if any of the following criteria apply:

Medical Conditions:

1. History of severe adverse reaction associated with a vaccine and/or severe allergic reaction (eg, anaphylaxis) to any component of 20vPnC, any other diphtheria toxoid-containing vaccine, or SIIV.
2. Allergy to egg proteins (egg or egg products) or chicken proteins.
3. Serious chronic disorder, including metastatic malignancy, severe COPD requiring supplemental oxygen, end-stage renal disease with or without dialysis, cirrhosis of the liver, clinically unstable cardiac disease, or any other disorder that in the investigator's opinion would make the participant inappropriate for entry into the study.
4. History of Guillain-Barré syndrome.
5. History of microbiologically proven invasive disease caused by *S pneumoniae*.
6. Known or suspected immunodeficiency or other conditions associated with immunosuppression, including, but not limited to, immunoglobulin class/subclass deficiencies, generalized malignancy, HIV infection, leukemia, lymphoma, or organ or bone marrow transplant.

7. Bleeding diathesis or condition associated with prolonged bleeding that would, in the opinion of the investigator, contraindicate intramuscular injection.
8. Congenital, functional, or surgical asplenia.
9. Other medical or psychiatric condition, including recent (within the past year) or active suicidal ideation/behavior, or laboratory abnormality that may increase the risk of study participation or, in the investigator's judgment, make the participant inappropriate for the study.

Prior/Concomitant Therapy:

10. Previous vaccination with any investigational pneumococcal vaccine, or planned receipt of any licensed or investigational pneumococcal vaccine through study participation.
11. Vaccination with any influenza vaccine <6 months before investigational product administration, or planned receipt of any licensed or investigational nonstudy influenza vaccine during study participation.
12. Currently receives treatment with immunosuppressive therapy, including cytotoxic agents or systemic corticosteroids, or planned receipt through the last blood draw (Visit 3). If systemic corticosteroids have been administered short term (<14 days) for treatment of an acute illness, participants should not be enrolled into the study until corticosteroid therapy has been discontinued for at least 28 days before investigational product administration. Inhaled/nebulized, intraarticular, intrabursal, or topical (skin, eyes, or ears) corticosteroids are permitted.
13. Receipt of blood/plasma products or immunoglobulin within the 60 days before investigational product administration, or planned receipt through the last planned blood draw in the study (through Visit 3).

Prior/Concurrent Clinical Study Experience:

14. Participation in other studies involving investigational drugs, investigational vaccines, or investigational devices within 28 days prior to study entry and/or during study participation. Participation in purely observational studies is acceptable.

Diagnostic Assessments:

Not applicable.

Other Exclusions:

15. Investigator site staff or Pfizer employees directly involved in the conduct of the study, site staff otherwise supervised by the investigator, and their respective family members.

5.3. Lifestyle Considerations

5.3.1. Contraception

The investigator or his or her designee, in consultation with the participant, will confirm that the participant has selected an appropriate method of contraception for the individual participant and his or her partner(s) from the permitted list of contraception methods **CCI** and will confirm that the participant has been instructed in its consistent and correct use. At time points indicated in the SoA, the investigator or designee will inform the participant of the need to use highly effective contraception consistently and correctly and document the conversation and the participant's affirmation in the participant's chart (participants need to affirm their consistent and correct use of at least 1 of the selected methods of contraception). In addition, the investigator or designee will instruct the participant to call immediately if the selected contraception method is discontinued or if pregnancy is known or suspected in the participant or partner.

5.4. Screen Failures

Screen failures are defined as participants who consent to participate in the clinical study but are not subsequently randomly assigned to study intervention/enrolled in the study. A minimal set of screen failure information is required to ensure transparent reporting of screen failure participants to meet the CONSORT publishing requirements and to respond to queries from regulatory authorities. Minimal information includes demography, screen failure details, eligibility criteria, and any AEs and SAEs.

Individuals who do not meet the criteria for participation in this study (screen failures) may not be rescreened.

5.5. Criteria for Temporarily Delaying Enrollment/Randomization/Study Intervention Administration

The following conditions may allow a participant to be vaccinated once the conditions have resolved and the participant is otherwise eligible:

5.5.1. Temporary Delay Criteria

The following conditions are temporary or self-limiting and a participant may be vaccinated in the study once the condition(s) has/have resolved and no other exclusion criteria are met.

The Visit 1 and Visit 2 blood draws prior to vaccination should take place on the same day as the vaccination.

5.5.1.1. Criteria for Temporarily Delaying Vaccine Administration

- Current febrile illness (body temperature $\geq 100.4^{\circ}\text{F}$ [$\geq 38.0^{\circ}\text{C}$]) or other acute illness within 48 hours before investigational product administration.
- Receipt of any inactivated or otherwise nonlive vaccine within 14 days or any live vaccine within 28 days before investigational product administration.

- Receipt of short-term (<14 days) systemic corticosteroids. Investigational product administration should be delayed until systemic corticosteroid use has been discontinued for at least 28 days. Inhaled/nebulized, intraarticular, intrabursal, or topical (skin, eyes, or ears) corticosteroids are permitted.

6. STUDY INTERVENTION

Study intervention is defined as any investigational intervention(s), marketed product(s), placebo, medical device(s), or study procedure(s) intended to be administered to a study participant according to the study protocol.

For the purposes of this protocol, the term investigational product may be used synonymously with study intervention.

6.1. Study Intervention(s) Administered

20vPnC and saline will be provided by the sponsor to the study sites (see Section 6.1.1 for SIIV supply).

20vPnC and saline will be packed and labeled as investigational product in accordance with current guidelines and applicable local and legal regulatory requirements. The formulations of the investigational products are described below.

20vPnC is a sterile liquid suspension formulation containing saccharides from pneumococcal serotypes 1, 3, 4, 5, 6A, 6B, 7F, 8, 9V, 10A, 11A, 12F, 14, 15B, 18C, 19A, 19F, 22F, 23F, and 33F individually conjugated to CRM₁₉₇. CCI

20vPnC will be supplied to the site as packaged, single-use prefilled syringes.

The saline control will consist of a sterile normal saline solution for injection (0.9% sodium chloride injection) and will be supplied to the site as packaged single-use prefilled syringes.

6.1.1. Concomitant Vaccines/Medications

Licensed SIIV containing strains of influenza viruses that are antigenically equivalent to the annually recommended strains will be supplied to the site as packaged, single-use prefilled syringes after required regulatory and legal documents have been received by the sponsor. Pfizer will provide this vaccine. CCI

CCI

Administration of SIIV will be recorded in the CRF.

6.1.2. Administration

At Visit 1, all participants will receive a single dose of SIIV injected intramuscularly into the right deltoid. The SIIV will be administered in an open-label fashion. Participants randomized to the (SIIV+20vPnC)/saline group will receive 0.5 mL of 20vPnC injected intramuscularly into the left deltoid, and participants randomized to the (SIIV+saline)/20vPnC group will receive 0.5 mL of saline injected intramuscularly into the left deltoid.

At Visit 2, participants randomized to the (SIIV+20vPnC)/saline group will receive 0.5 mL of saline intramuscularly into the left deltoid, and participants randomized into the (SIIV+saline)/20vPnC group will receive 0.5 mL of 20vPnC injected intramuscularly into the left deltoid.

The 20vPnC and saline vaccines will be administered by an unblinded third-party site staff member at Visit 1 and Visit 2.

Standard vaccination practices must be observed, and the vaccine must not be injected into the blood vessels. Appropriate medication and other supportive measures for management of an acute hypersensitivity reaction should be available in accordance with local guidelines for standard immunization practices.

Administration of study interventions should be performed by an appropriately qualified, GCP-trained, and vaccine-experienced member of the study staff (eg, physician, nurse, physician's assistant, nurse practitioner, pharmacist, or medical assistant) as allowed by local, state, and institutional guidance.

Study intervention administration details will be recorded on the CRF.

6.1.3. Medical Devices

In this study, medical devices being deployed are the prefilled syringes containing 20vPnC, saline, or SIIV. Instructions for medical device use are provided in the IP manual or in the package insert.

Medical device incidents, including those resulting from malfunctions of the device, must be detected, documented, and reported by the unblinded study personnel throughout the study.

CCI

6.2. Preparation/Handling/Storage/Accountability

The investigator or an approved representative, eg, pharmacist, will ensure that all investigational products are stored in a secured area with controlled access under required storage conditions and in accordance with applicable regulatory requirements.

Investigational products should be stored in their original containers and in accordance with the labels.

CCI

[REDACTED]

[REDACTED]

[REDACTED]

[REDACTED]

[REDACTED]

CCI

[REDACTED]

[REDACTED]

CCI [REDACTED]

6.2.1. Preparation and Dispensing

See the IP manual or applicable SRSD for instructions on how to prepare the study intervention for administration. Study interventions should be prepared and dispensed by an appropriately qualified and experienced member of the study staff (eg, physician, nurse, physician's assistant, nurse practitioner, pharmacy assistant/technician, or pharmacist) as allowed by local, state, and institutional guidance. The 20vPnC and saline will be prepared and administered by an unblinded staff member (see Section 6.2.2).

6.2.2. Preparation/Handling by Unblinded Staff

The 20vPnC and saline will be prepared by qualified unblinded site personnel according to the IP manual and will be administered by an unblinded site staff member at Visit 1 and Visit 2. All other site staff members, including the PI, and the participant will be blinded. The PI will assign the responsibility of administering 20vPnC and saline to unblinded persons who will not participate in the evaluation of any study participant. More than 1 unblinded site staff member will be assigned. A site staff member or clinic pharmacy should fulfill this role and must be an appropriately qualified and experienced member of the study staff as described in Section 6.2.1. Contact between the unblinded site staff member who will administer 20vPnC and saline and study participants should be kept to a minimum.

6.3. Measures to Minimize Bias: Randomization and Blinding

As the appearances of 20vPnC and saline are different, the investigational products will be prepared and administered by a designated third-party unblinded site staff member. All other study personnel, including the PI, and the participant will be blinded. The unblinded site staff member(s) will not participate in participant assessments. Because all participants will receive SIV at Visit 1, SIV will be an open-label vaccination but can still be prepared and administered by the same designated third-party unblinded site staff member. See [Section 6.3.2](#) and [Section 6.3.3](#) for more details on blinding of site staff members and sponsor.

6.3.1. Allocation to Study Intervention

Allocation (randomization) of participants to vaccine groups will proceed through the use of an IRT system (IWR). The site staff (study coordinator or specified designee) will be required to enter or select information, including, but not limited to, the user's ID and password, the protocol number, and the participant number. The site staff will then be

provided with a vaccine assignment, randomization number, and DU or container number when the investigational product is being supplied via the IRT system. The IRT system will provide a confirmation report containing the participant number, randomization number, and DU or container number assigned. The confirmation report must be stored in the site's files.

The study-specific IRT reference manual and IP manual will provide the contact information and further details on the use of the IRT system.

Participants will be stratified by prior pneumococcal vaccine status (no previous pneumococcal vaccine [naïve], receipt of at least 1 dose of PPSV23 only or at least 1 dose of 13vPnC only, or receipt of at least 1 dose of both PPSV23 and 13vPnC) and randomized in a 1:1 ratio to each of the 2 vaccine groups, either the coadministration group ([SIIV+20vPnC]/saline) or the separate-administration group ([SIIV+saline]/20vPnC group), by center-based randomization. Investigators will remain blinded to each participant's assigned study intervention throughout the course of the study. In order to maintain this blind, an otherwise uninvolved third party will be responsible for the preparation and dispensing of all study intervention and will endeavor to ensure that there are no differences in time or effort taken to administer the study intervention and no blinded site staff are able to view the administration.

This third party will instruct the participant to avoid discussing the packaging of the study intervention with the investigator.

In the event of a Quality Assurance audit, the auditor(s) will be allowed access to unblinded study intervention records at the site(s) to verify that randomization/dispensing has been done accurately.

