4. STUDY DESIGN

4.1. Overall Design

[figure not shown]
This Phase 3, multicenter, randomized, double-blind study, with a 2-arm parallel design, will be conducted at investigator sites in the United States. The purpose of this study is to assess the safety and immunogenicity of 20vPnC and SIIV when given together at the same visit ([SIIV+20vPnC]/saline group) compared to 20vPnC given 1 month after SIIV ([SIIV+saline]/20vPnC group). The study design and assessments are modeled from prior studies of pneumococcal conjugate vaccine coadministered with influenza vaccine.^{68,69,70}

CCI [REDACTED]

Approximately 1780 healthy adults ≥ 65 years of age will be stratified by prior pneumococcal vaccine status (no previous pneumococcal vaccine [naïve], receipt of at least 1 dose of PPSV23 only, receipt of at least 1 dose of 13vPnC only, or receipt of at least 1 dose each of PPSV23 and 13vPnC) and randomized in 1:1 ratio to 1 of 2 groups by center-based randomization. The coadministration group ([SIIV+20vPnC]/saline) will receive SIIV and 20vPnC at the same visit (Visit 1), followed 1 month later by administration of saline (Visit 2). The separate-administration group ([SIIV+saline]/20vPnC) will receive SIIV and saline at Visit 1, followed 1 month later with 20vPnC administered at Visit 2.

Refer to [Section 4.2](#) for the rationale behind this stratification.

If participants have received prior pneumococcal vaccination(s), the most recent dose must have been given ≥ 6 months prior to the first study vaccination. Information on any prior pneumococcal vaccines will be collected at enrollment. **CCI**

On Day 1 (Visit 1), participants will be assessed for eligibility (including medical history and pneumococcal vaccine history). If eligible, participants will have blood drawn for immunogenicity assessments and be randomized to receive either SIIV and 20vPnC ([SIIV+20vPnC]/saline) or SIIV and saline ([SIIV+saline]/20vPnC). The 20vPnC and saline will be prepared and administered by an unblinded investigator site staff member. Participants will be observed for 30 minutes after vaccination by blinded investigator site staff, and any reactions occurring during that time will be recorded as AEs.

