5.1. Inclusion Criteria

Participants are eligible to be included in the study only if all of the following criteria apply:

Age and Sex:

1. Male or female participants ≥ 65 years of age at the time of consent.

Type of Participant and Disease Characteristics:

2. Participants who are willing and able to comply with all scheduled visits, treatment plan, laboratory tests, lifestyle considerations, and other study procedures.
3. Adults determined by clinical assessment, including medical history and clinical judgment, to be eligible for the study, including adults with preexisting stable disease, defined as disease not requiring significant change in therapy in the previous 6 weeks or hospitalization for worsening disease within 12 weeks before receipt of investigational product.
4. Expected to be available for the duration of the study and can be contacted by telephone during study participation.

5. Male participant who is able to father children and willing to use a highly effective method of contraception, as outlined in this protocol, for at least 28 days after the dose of investigational product; or female participant not of childbearing potential; or male participant not able to father children. Refer to Appendix 4 for reproductive criteria for male (Section 10.4.1) and female (Section 10.4.2) participants.

CCI

6. Adults who have no history of ever receiving a pneumococcal vaccine (ie, pneumococcal vaccine-naïve), or have a history of receiving a licensed pneumococcal vaccination ≥ 6 months prior to the first vaccination in the study.

Note: For participants with a history of receiving a licensed pneumococcal vaccination, documentation of date(s) and type(s) of prior pneumococcal vaccination(s) will be obtained.

Informed Consent:

7. Capable of giving signed informed consent, as described in Appendix 1, which includes compliance with the requirements and restrictions listed in the ICD and in this protocol.

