6.6. Recording Prior and Concomitant Vaccines and Concomitant Treatments

The name and date of administration of any prior pneumococcal vaccines will be collected and recorded in the CRF. The name(s) and date(s) of administration are to be obtained from sources, such as medical records or vaccination cards.

The name and date of administration for all nonstudy vaccinations received from the time of signing of the ICD to Visit 3 will be collected and recorded in the CRF.

Medications taken to treat SAEs or NDCMCs from the time of signing of the ICD to Visit 4 will be recorded in the CRF.

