8.11.1. Visit 1 (Vaccination 1 – Day 1)

Prior to randomization:

- Obtain a personally signed and dated ICD indicating that the participant has been informed of all pertinent aspects of the study before performing any study-specific procedures.
- Assign a participant number via the IRT.
- Obtain and record the participant's demographic information (including date of birth, sex, race, and ethnicity). The complete date of birth (ie, DD-MMM-YYYY) will be collected to critically evaluate the immune response and safety profile by age.
- Obtain and record significant medical history, including the presence of chronic conditions (eg, diabetes, asthma, cardiac disease, COPD), and/or medical history of significance, such as relevant surgical procedures.
- Perform a clinical assessment. If the clinical assessment indicates that a physical examination is necessary to comprehensively evaluate the participant, perform a physical examination and record any findings in the source documents and, if significant, record such findings on the medical history CRF.
- Record pneumococcal vaccine history, including name(s) of the vaccine(s) received and date(s) given (dates may be approximate but minimally sufficient to confirm eligibility and appropriate stratification).
- Assess and record smoking history.
- If applicable, instruct the participant to use appropriate contraceptives until 28 days after administration of the last dose of investigational product, and document the conversation and the participant's affirmation in the participant's source document.
- Measure and record the participant's oral temperature (°F/°C).
- Ensure and document that all of the inclusion criteria and none of the exclusion criteria are met and that none of the temporary delay criteria are met.
- Assign a randomization number and an investigational product container number via the IRT. This must be the last step before proceeding. An unblinded site staff member will prepare the investigational product according to the IP manual.

After randomization:

- Collect a blood sample of approximately 30 mL for immunogenicity assessments prior to vaccination.
- Administer a single 0.5-mL injection of SIIV into the right deltoid muscle.
- An unblinded site staff member will administer a single 0.5-mL injection of 20vPnC or saline into the left deltoid muscle.

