5.2.2.2. Geometric Mean Ratios

Model-Based GMR

As the primary approach to calculate the GMR and CI for each serotype of OPA titer 1 month after 20vPnC, a linear regression model that includes terms for prior pneumococcal vaccine status, age at vaccination at Visit 1, corresponding baseline OPA titer, sex, smoking status, and vaccine group will be used to calculate the serotype-specific OPA GMR and the associated 95% CI, along with the model-based LS GMTs and associated 2-sided 95% CIs for each vaccine group.

As the primary approach to calculate the GMR and CI for each strain of HAI titer 1 month after SIIV, a linear regression model that includes terms for prior pneumococcal vaccine status, age at vaccination at Visit 1, corresponding baseline HAI titer, sex, smoking status, and vaccine group will be used to calculate the strain-specific HAI GMR and the associated 95% CI, along with the model-based LS GMTs and associated 2-sided 95% CIs for each vaccine group.

CCI [REDACTED]

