6.1.2.2. Strain-Specific HAI Titers 1 Month After Vaccination With SIIV

6.1.2.2.1. Main Analysis

- Estimand: GMR of the strain-specific HAI titers 1 month after vaccination with SIIV from the coadministration group to the corresponding strain from the separate-administration group ([Section 2.1](#)).
- Analysis set: Evaluable HAI immunogenicity population. CCI [REDACTED]
- Analysis time point: 1 Month after vaccination with SIIV. One month after vaccination refers to 1 month after vaccination with SIIV (Visit 2) for both vaccine groups.
- Analysis methodology: Linear regression model that includes terms for prior pneumococcal vaccine status, age (at vaccination at Visit 1), corresponding baseline HAI titer, sex, smoking status (current smoker, ex-smoker, never smoked), and vaccine group ([Section 5.2.2.2](#)). NI for strain-specific HAI will be declared if the lower bound of the 2-sided 95% CI for the GMR of the coadministration group to the separate-administration group is greater than 0.67 (1.5-fold criterion).
- Intercurrent events and missing data: Missing serology results will not be imputed. Titers below LLOQ or denoted as BLQ will be set to $0.5 \times \text{LLOQ}$ for analysis.
- Reporting results: The LS GMTs and associated 95% CIs for strain-specific HAI titers from each vaccine group, as well as the model-based HAI GMRs with their associated 95% CIs, will be summarized separately for each strain of HAI titer.

Figures:

A forest plot of GMRs with 95% CIs for all strains, with a vertical reference line corresponding to a GMR of 0.67, will be presented.

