6.5. Baseline and Other Summaries and Analyses

6.5.1. Baseline Summaries

6.5.1.1. Demographic Characteristics

Demographic characteristics, including age, sex, race, ethnicity, and prior pneumococcal vaccine status, will be summarized by vaccine group for all participants in the safety population and evaluable immunogenicity populations. Descriptive statistics (n and %) will be provided for overall and subgroup tables.

CCI [REDACTED]

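### Does the three-stratum wording in Protocol 6.3.1, against four strata in Protocol 4.1 and SAP 2.2, call for a change to the plan?

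*Protocol*

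**What the plan says.** Protocol 4.1 (Overall Design) stratifies by prior pneumococcal vaccine status and, after the naive category, continues "receipt of at least 1 dose of PPSV23 only, receipt of at least 1 dose of 13vPnC only, or receipt" of both vaccines. SAP 2.2 (Study Design) gives the same list. Each category has its own comma and its own opening words, so there are four.

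Protocol 6.3.1 (Allocation to Study Intervention) instead has "receipt of at least 1 dose of PPSV23 only or at least 1 dose of 13vPnC only, or receipt" of both. The comma and the repeated opening words between the two single-vaccine categories are gone, which gives three categories if read literally.

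The same variable is used in the analysis. SAP 5.2.2.2 specifies, for OPA, "a linear regression model that includes terms for prior pneumococcal vaccine status, age at vaccination at Visit 1, corresponding baseline OPA titer" and further terms. SAP 6.1.2.2.1 specifies, for HAI, a "Linear regression model that includes terms for prior pneumococcal vaccine status" and further terms. SAP 6.5.1.1 puts the variable in the baseline table: "Demographic characteristics, including age, sex, race, ethnicity, and prior pneumococcal vaccine status, will be summarized by vaccine group".

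The source data are detailed. Protocol 5.1 says that "documentation of date(s) and type(s) of prior pneumococcal vaccination(s) will be obtained", Protocol 6.6 that "The name and date of administration of any prior pneumococcal vaccines will be collected and recorded in the CRF", and Protocol 8.11.1 allows that "dates may be approximate but minimally sufficient to confirm eligibility and appropriate stratification".

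**The concern.** The interactive response system can carry only one set of strata, and the section that departs from the others is the one that describes allocation. Pooling all single-vaccine histories is a conceivable design, so the wording cannot be dismissed on sight as a typing error. Protocol 4.2 also treats the two histories differently: it reports lower responses to conjugate vaccine after PPSV23 and variable responses after a second 13vPnC dose. If they were pooled, the arms could differ by chance in the mix of the two.

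The SAP model descriptions list the levels of smoking status but not those of prior vaccine status, so a programmer has to take them from elsewhere. At stake are designed balance between the two single-vaccine histories and the use of one factor throughout randomisation, models and baseline table.

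**Working it through.** **1. Count the strata.** Protocol 4.1: four. SAP 2.2: four. Protocol 6.3.1: three as punctuated, although it still attaches its own minimum dose and its own restriction to each vaccine. Two statements agree and one departs.

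**2. Sample size.** Protocol 9.2 uses 800 evaluable per group and 10% nonevaluable. 800 / (1 − 0.10) = 888.9, so 889 per group and 1778 in total, against a stated figure of about 1780. It reproduces, and the number of strata does not enter it. The inputs to the power simulations are redacted, so power was not recomputed.

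**3. Degrees of freedom.** With four status levels the OPA model has intercept 1, group 1, status 3, age 1, baseline titer 1, sex 1 and smoking 2, which makes 10 parameters and 1600 − 10 = 1590 residual df. With three levels there are 1591. The t critical value is 1.96146 in both cases.

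**4. The possible combinations.**
- Four strata, four model levels: the two histories are balanced by design and adjusted for.
- Three strata, four model levels: chance imbalance between the histories is adjusted for.
- Three strata, three model levels: imbalance is not adjusted for. It averages zero and the interval is slightly wider.
- Four strata, three model levels: the histories are balanced by design and the interval is slightly wider.

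Only the third can move an estimate. It needs three strata in the allocation system and three levels in the model, and the documents do not state that combination.

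**5. Size of the third case (OPA).** Assumed inputs, because Protocol 2.6 targets no proportions: 900 of 1600 evaluable participants in the pooled stratum (450 per arm), a 50:50 split, a 2-fold GMT difference between the histories, residual SD 1.5 on the natural-log scale, and baseline titer independent of history.
- SD of the difference in ln(GMR) between three- and four-level models: √(2 × 0.25/450) × ln 2 × 900/1600 = 0.0333 × 0.693 × 0.5625 = 0.0130. A simulation of 1,500 trials gave 0.0130 with mean 0.0002.
- Relative to the margin: 0.0130/0.693 = 1.9%.
- Half-width with four levels: 1.96146 × 1.5 × √(2/800) = 0.147.
- Widening factor with three levels: √(1 + 0.5625 × 0.25 × (ln 2)²/1.5²) = 1.015, so the half-width is 0.149. The simulation gave 0.1496 against 0.1475.
- Smallest observed GMR that passes the 0.5 criterion: exp(−0.693 + 0.147) = 0.579 with four levels and exp(−0.693 + 0.149) = 0.581 with three.

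**6. Range.**
- High corner (1200 pooled, 50:50, 3-fold, residual SD 1.0): √(2 × 0.25/600) × ln 3 × 0.75 = 0.024, and the widening factor is √(1 + 0.75 × 0.25 × (ln 3)²) = 1.107. That is 10.7% of a half-width of 1.96146 × 1.0 × 0.05 = 0.098, still small beside 0.693.
- Low corner (400 pooled, 20:80, 1.5-fold): √(2 × 0.16/200) × ln 1.5 × 0.25 = 0.004. At residual SD 2.0 the widening factor is √(1 + 0.25 × 0.16 × (ln 1.5)²/2²) = 1.0008.

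If baseline titer tracks vaccine history, these figures shrink, because baseline titer is itself in the model.

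**7. HAI.** The visible text does not link pneumococcal vaccine history to influenza response, so no effect is claimed there.

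**The case for a change.** The strongest case for acting is that the inconsistency can be verified by counting and sits in the operative section. It concerns a factor that the sponsor thought worth stratifying on, and it would cost only a document check and a corrected parenthesis. The model sections do not list the levels.

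What stands: the wording mismatch is real, the allocation system's specification is not among the documents, and a reader cannot tell from the visible text which scheme was programmed. Parts of Protocol 4.2 and SAP 3.4 are redacted, so a clarification may exist there.

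What does not stand is any consequence for the analysis. The analyst works from the SAP, whose one visible definition has four levels, and the CRF supports those levels whatever was programmed. The numerical effect appears only if that definition is ignored and the allocation system also has three strata. Rewording every passage to match the system could even do harm: with a three-stratum system, it would remove from SAP 2.2 the four-level definition that makes the model term clear. Moving the system itself from three strata to four would thin the centre-by-stratum cells. With an assumed 20 centres, the average cell falls from 1780/20/3 = 29.7 to 1780/20/4 = 22.3 participants, for a balance that the model already supplies.

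**Conclusion.** The difference is a wording slip in one parenthesis of Protocol 6.3.1, plus a gap in the level listing that SAP 2.2 already fills. Randomisation and the noninferiority tests are valid with three strata or four, expected bias is zero, and sample size, alpha and margins are untouched. With the four-level term the effect on the primary results is nil beyond one residual degree of freedom. In the unfavourable and unstated case of three levels throughout, ln(GMR) moves by an SD of about 0.013 (0.004 to 0.024 over the range tried) and the interval widens by 1.5% (0.1% to 10.7%).

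These sizes rest on assumed stratum shares, history effects and residual SDs. The conclusion does not: it rests on the validity of either randomisation and on the four-level definition in the SAP. Confirming the programmed strata and tidying the parenthesis is housekeeping. It changes no result, and no change to the plan is needed.
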